2.2. Background

The covid-19 pandemic represents an historic event with the potential to cause enormous psychological distress both because of the fear of the virus and its health implications, and because it requires major life adjustments (i.e. social distancing, isolation, unemployment etc.) which pose further strain on people's mental health. A recent review of the available literature reported that in the general population symptoms of distress and self-reported stress (8-28%) are common psychological reactions to the COVID-19 pandemic. A survey including 52,730 participants living in the Wuhan region in China, found that 35% of the respondents experienced psychological distress.

How individuals respond to stressful and traumatic experiences over time have been evaluated in longitudinal studies aiming at identifying stress and resilience trajectories. Evidence supports an adapting response with most individuals showing patterns of resilience and gradual recovery (3). However, about 38% of people experiencing traumatic and stressful situations show persistent chronic stress or a delayed stress response. Even though these studies have been helpful in pointing out that most people are indeed resilient, they present several limitations due to the use of traditional assessment methods. Such measures are collected infrequently and require participants to recall past events, feelings, and states, increasing the likelihood of bias and

limiting the ability to detect points of inflection where actual change occurs. Thus, little is known about specific turning points in these trajectories and possible predictors of such turning points in both observational and interventional studies.

Ecologically valid assessment methods have been developed to address the issues represented by the customary recall measures. Ecological Momentary Assessment (EMA) involves measuring psychological processes repeatedly in real time as they occur in the natural environment. EMA encompasses diverse assessment techniques including diaries, behavioral observation, and self-monitoring. EMA presents the advantage of minimizing recall bias, while improving generalizability and ecological validity. It also allows the identification of microprocesses that influence behaviors in real-world contexts.

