9.3. Analysis Sets

9.4. Statistical Analyses

Primary outcome.

- *Quantitative analysis.* Feasibility of the intervention will be reported as descriptive statistics, focusing on number of individuals who contact the study team with interest in participation; the number of eligible individuals after the initial screening; time taken to recruit the sample; retention rates; the rate of EMA survey completion. Acceptability will be measured as means and standard deviations of responses to each item within the satisfaction questionnaire, and the proportion of participants giving favorable responses.
- *Qualitative analysis.* A codebook and coding guidelines will be developed for analysis of qualitative feedback. Two researchers will code all transcripts using [REDACTED] and add to the codebook as needed. Each researcher will then independently identify main themes. Results will be compared and discussed until an agreement will be reached. Representative samples of feedback from open-ended questions will be also used.

Secondary outcomes.

- *Standard responses.* Sociodemographic responses will be described by mean, standard deviation (SD), and range. Mixed-effects models for repeated measure (MMRM) will be used to examine change in secondary outcomes, with outcomes examined as change in scores between baseline and follow-up. Models will include effects for time, group (control/intervention), group x time interactions and baseline values of the outcome variable (to control regression to the mean) and other potential confounders. Per Protocol analysis will be performed. The per protocol population will include all randomized participants excluding those who had protocol violations. A significance level of 0.05 will be used. All analyses will be performed using [REDACTED]

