- *EMA responses.* Variability in momentary responses will be described by each participant's mean, SD, and range of mean square successive difference (34), which is a measure of variability that accounts for the temporal order of responses. Analyses on momentary responses will be conducted using Multilevel Modelling (35) because of the hierarchical structure of the data (level 1 = measurement time, level 2 = measurement day, level 3 = participant) and the aptness for dealing with varying time intervals between assessments and missing data. For depicting systematic (i.e. changing with time) or unsystematic (i.e. symptom variability) inter- and intraindividual variations in symptom severity and coping strategies, intraclass correlation coefficients (ICCs) will be used, while associations of symptomatology, coping efficacy and HCC will be analyzed using multilevel correlation and regression analyses.

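### The EMA plan gives systematic versus unsystematic change to ICCs, but with no time term stated an ICC ignores the order of days, and no planned EMA summary measures systematic change

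*Combined protocol and SAP*

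**What the plan says.** In section 9.4 (EMA responses), each participant's momentary responses are first described by mean, SD and the MSSD, "which is a measure of variability that accounts for the temporal order of responses". Then: "Analyses on momentary responses will be conducted using Multilevel Modelling (35) because of the hierarchical structure of the data", with "level 1 = measurement time, level 2 = measurement day, level 3 = participant". The next sentence sets the task at issue: "For depicting systematic (i.e. changing with time) or unsystematic (i.e. symptom variability) inter- and intraindividual variations in symptom severity". It extends the task to coping as well, and the tool it names for both is this: "intraclass correlation coefficients (ICCs) will be used". Regression has a different job in that sentence: "associations of symptomatology, coping efficacy and HCC will be analyzed using multilevel correlation and regression analyses".

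No fixed effect of day, random slope or group-by-time term is written for the EMA model. Such terms appear in 9.4 only under Standard responses, for the survey scores: "Models will include effects for time, group (control/intervention), group x time interactions and baseline values of the outcome variable".

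Section 2.2 presents EMA as the answer to recall measures, which it criticises as "limiting the ability to detect points of inflection where actual change occurs". Under section 4.1, the intervention arm has one week of EMA alone and then two weeks of EMA with stress-management texts. Controls have three weeks of EMA with no change of phase.

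**The concern.** An ICC is a ratio of variance components. In a three-level model without time, a participant's days are exchangeable, so a decline over 21 days and haphazard daily variation both enter the day-level component. The quantity that the plan calls systematic is defined by time, and the statistic named for it does not use the order of time.

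The interpretation of the EMA data is at stake. If the ICCs come from a model without time, a response that begins when the texts start in the intervention arm would sit in day-level variance, and nothing in the stated plan would separate it from symptom variability. The EMA data could show when change occurs, which is the reason section 2.2 gives for collecting them, but no stated EMA summary would extract it.

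**Working it through.** The plan states no ICC, variance component or EMA effect size, so there is no figure to reproduce. The check applies the named statistic to the trial's own layout.

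**Inputs from the documents.** N = 70 participants (section 5), D = 21 days and M = 2 prompts per day (section 4.1), giving 42 responses per person if complete.

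**Assumed inputs, not in the documents.** Person variance 1, day variance v = 0.5, moment variance 1, complete data.

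**Estimator.** Nested ANOVA components:
- moment = MS_moment
- day = (MS_day − MS_moment)/M
- person = (MS_person − MS_day)/(D × M)

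MS_day is a sum of squared deviations of a person's day means from that person's own mean. Reordering the days leaves every term unchanged, so the ICCs are unchanged whatever the variances.

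**Expected shares.**
- Pure day noise: components 1, 0.5, 1; total 2.5; shares 0.40/0.20/0.40 (person/day/moment).
- Pure linear decline common to all, variance 0.5 over the 21 days: day = 0.5 × 21/20 = 0.525; person = 1 − 0.525/21 = 0.975; moment = 1; total 2.5; shares 0.39/0.21/0.40.
- Size of that decline: the SD of the day index is √((21² − 1)/12) = 6.055, so the slope is −0.707/6.055 = −0.117 per day, or 20 × 0.117 = 2.3 momentary SDs in total.
- A single drop at the end of week 1 (7 days before, 14 after) has the same variance if δ² × (7/21) × (14/21) = 0.5, so δ = 1.5. It gives the same 0.39/0.21/0.40.

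**Range.** The trend-versus-noise gap in the day share is (v/20)/(total variance). With person and moment variance 1, it is 0.005/2.1 = 0.002 at v = 0.1, 0.025/2.5 = 0.010 at v = 0.5, 0.05/3 = 0.017 at v = 1 and 0.1/4 = 0.025 at v = 2. For any variances it stays below 1/20 = 0.05.

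**Simulation** (70 × 21 × 2, 500 replicates, v = 0.5):

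| Pattern | Person ICC | Day share | Same-day ICC | MSSD | Mean slope per day |
|---|---|---|---|---|---|
| Linear decline | 0.389 | 0.210 | 0.599 | 2.01 | −0.117 |
| Same data, days shuffled | 0.389 | 0.210 | 0.599 | 2.51 | 0.000 |
| Random day noise | 0.399 | 0.199 | 0.599 | 2.48 | 0.000 |

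In the one dataset compared directly, the ICCs before and after shuffling agreed to every printed digit.

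**What the MSSD adds.** Of the 41 successive differences, 21 are within a day and 20 cross days. The expected MSSD is 2 + (20/41) × 0.117² = 2.007 for the decline and 2 + (20/41) × (2 × 0.5) = 2.488 for noise. It separates the two patterns. The slope enters squared, however, so a rise of 0.117 per day also gives 2.007.

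**With a time term.** After each person's linear slope is removed, the remaining day share is about 0 for the decline (−0.014, slightly negative because the degrees of freedom for the slope were not adjusted) and 0.183 for noise. The slope term does the separating.

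**The case against.** - **The MSSD is order-sensitive and stands in the same section.** This is correct. A reader might infer that someone who improves and someone who merely fluctuates are described identically by the plan. The documents do not support that: the MSSD is about 2.01 for the decline and 2.48 for noise. What remains is that the plan assigns the MSSD to variability, and it cannot tell improvement from worsening or say when change occurred.
- **The plan does not say that the model is empty.** This is also correct. Multilevel modelling is chosen partly because it handles uneven time intervals, and it can carry time effects. ICCs conditional on time are legitimate. A reader might infer that ICCs are the wrong tool altogether, which goes too far. But no time term is written, and if one were, the slope and not the ICC would measure systematic change.
- **The consequence is limited.** Section 9.1 rests on survey completion and retention. Group differences over follow-up are addressed by the repeated-measures model, which has time and group-by-time terms. No listed objective asks for EMA trajectories, and section 2.2 is motivation rather than an estimand. All of this stands, and it limits the weight of the point. The repeated-measures model uses the survey time points, so it does not supply the within-period EMA description.
- **The illustration is one chosen case.** The variances are assumed, and making all day-level variance a common linear decline is extreme. The numbers say nothing about the likely size in this trial. The order-invariance is algebraic and does not rest on them.

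**Conclusion.** The point holds for the ICC as specified. Taken from the moment/day/participant hierarchy without a time term, it cannot separate change over time from unsystematic variation, and no other EMA summary in section 9.4 is assigned to that task or gives direction or timing. In the assumed case the person/day shares differ by only 0.01 between a decline of 2.3 momentary SDs and no change at all. With the ANOVA estimator, complete data and a common linear trend matched on variance, the gap in the day share is below 0.05 for any variances.

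The conclusion assumes that the ICCs are computed without time effects, as the text reads. If time effects are intended, the remedy is to write them down. The point bears on a secondary, exploratory analysis. A reader might infer that it weakens the feasibility conclusions or the choice of 70 participants; neither depends on the EMA ICCs.

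**What to change.** In section 9.4 (EMA responses):

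1. Add to the EMA multilevel model a fixed effect of study day, or of phase with the change at the end of EMA week 1, together with its interaction with group and a participant-level random slope. The interaction is needed because only the intervention arm changes phase; a pooled slope would not isolate response to the texts.
2. Report the slopes or phase changes by group, and the slope variance, as systematic change.
3. Report day- and moment-level variances, ICCs and MSSD after removal of the trend as unsystematic variability.
4. Keep the unconditional ICC only for the split between and within persons.

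The cost is a few lines of text and slightly more analysis, with no new data. The random slope may need to be simplified if it does not converge with 70 participants, and the plan should say in advance how.

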9.4.1. Safety Analysis

All AEs will be coded by system organ class and Medical Dictionary for Regulatory Activities (MedDRA) preferred term. All AEs will be coded by system organ class and Medical Dictionary for Regulatory Activities (MedDRA) preferred term. All safety analyses will be made on the Safety Population. All safety analyses will be made on the Safety Population.

9.5. Interim Analysis

N/A

10. Supporting Documentation and Operational Considerations

10.1. Appendix 1: Regulatory, Ethical, and Study Oversight Considerations

10.1.1. Regulatory and Ethical Considerations

- This study will be conducted in accordance with the protocol and with the following:
 - Consensus ethical principles derived from international guidelines including the Declaration of Helsinki and Council for International Organizations of Medical Sciences (CIOMS) International Ethical Guidelines
 - Applicable ICH Good Clinical Practice (GCP) Guidelines
 - Applicable laws and regulations
- The protocol, protocol amendments, ICF, and other relevant documents (e.g., advertisements) must be submitted to an IRB/IEC by the investigator and reviewed and approved by the IRB/IEC before the study is initiated.
- Any amendments to the protocol will require IRB/IEC approval before implementation of changes made to the study design, except for changes necessary to eliminate an immediate hazard to study participants.
- Protocols and any substantial amendments to the protocol will require IRB/IEC approval prior to initiation except for changes necessary to eliminate an immediate hazard to study participants.
- The investigator will be responsible for the following:
 - Providing written summaries of the status of the study to the IRB/IEC annually or more frequently in accordance with the requirements, policies, and procedures established by the IRB/IEC
 - Notifying the IRB/IEC of SAEs or other significant safety findings as required by IRB/IEC procedures
 - Providing oversight of the conduct of the study at the site and adherence to requirements of 21 CFR, ICH guidelines, the IRB/IEC, and all other applicable local regulations.

10.1.2. Informed Consent Process

- Patients who meet the eligibility criteria will be asked to sign an online consent form. The consent form will describe the potential risks and benefits of study participation as well as the responsibilities of the participants and the investigators.
- Participants must be informed that their participation is voluntary. Participants are required to sign a statement of informed consent that meets the requirements of 21 CFR 50, local regulations, ICH guidelines, Health Insurance Portability and Accountability Act (HIPAA) requirements, where applicable, and the IRB/IEC or study center.
- Participants must be re-consented to the most current version of the ICF(s) during their participation in the study.
- A copy of the ICF(s) must be provided to the participant.

10.1.3. Data Protection

Study participants will be assigned a unique identifying number (ID). This ID, rather than any PII, will be used to label all hard copy and electronic data. Identifiers and study data will be saved in separate files, accessible only to study staff. As a result, the bulk of the data will be completely anonymized, including records of screening instruments.

[figure not shown]
However, the consent form and documentation of payment will include both the subject's name and ID. As a result, these documents will be stored separately from other records. All hard copy records will be stored in locked cabinets to which only the study investigators will have access. All electronic records will be stored on an electronically secure database at Click Therapeutics. This database is password protected.

10.1.4. Patient Privacy

Protection of Participant Privacy: Privacy in the context of this study includes confidentiality of data and personal information and in the handling and reporting of data. The investigator will be responsible for ensuring data are stored in a secure area accessible only to study staff. These provisions will be monitored periodically. Clinical research may be a stressful experience for some patients; therefore, sensitivity in recruitment (i.e., including no coercive strategies) will be a high priority.

HIPPA compliance: All projects will obtain an authorization for the Health Insurance Portability and Accountability Act (HIPAA) from the Institutional Review Board (IRB). The authorization is to use or disclose protected health information for research that also includes a research repository, which will be signed by the participant, with a copy kept in the data management system. A copy will also be available to the patient. This authorization will allow the use or sharing of private information including information that is given via written questionnaires from questions regarding demographic and psychological and medical information.

10.1.4.1. Medical Monitor

- Participant safety will be continuously monitored by the Medical Monitor, which includes safety signal detection at any time during the study.
- All safety data collected will be summarized and reviewed by the Medical Monitor for agreement of next steps.
- If at any time during the course of the study, the PI judges that risk to subjects outweighs the potential benefits, either shall have the discretion and responsibility to recommend that the study be terminated.
- Case unblinding may be performed for above reviews if necessary.

10.1.5. Dissemination of Clinical Study Data

[figure not shown]
N/A

10.1.6. Data Quality Assurance

- The investigator must permit study-related monitoring, audits, IRB/IEC review, and regulatory agency inspections and provide direct access to source data documents.
- The sponsor or designee is responsible for the data management of this study including quality checking of the data.

10.1.7. Source Documents

Source documents are defined as the electronic survey responses. Electronic survey responses provide evidence for the existence of the participant and substantiate the integrity of the data collected. Source documents for this study will be collected electronically and will be maintained by the sponsor.

10.2. Appendix 2: Clinical Laboratory Tests

Laboratory tests are not evaluated in this study.

10.3. Appendix 3: AEs and SAEs: Definitions and Procedures for Recording, Evaluating, Follow-up, and Reporting

10.3.1. Definition of AE

AE Definition

- An AE is any untoward medical occurrence in a clinical study participant, temporally associated with the use of study intervention, whether or not considered related to the study intervention.
- NOTE: An AE can therefore be any unfavorable and unintended sign (including an abnormal laboratory finding), symptom, or disease (new or exacerbated) temporally associated with the use of study intervention.

Events Meeting the AE Definition

- Any abnormal laboratory test results (hematology, clinical chemistry, or urinalysis) or other safety assessments (e.g., ECG, radiological scans, vital signs measurements), including those that worsen from baseline, considered clinically significant in the medical and scientific judgment of the investigator (i.e., not related to progression of underlying disease).
- Exacerbation of a chronic or intermittent pre-existing condition including either an increase in frequency and/or intensity of the condition.
- New conditions detected or diagnosed after study intervention administration even though it may have been present before the start of the study.
- Signs, symptoms, or the clinical sequelae of a suspected intervention- intervention interaction.
- Signs, symptoms, or the clinical sequelae of a suspected overdose of either study intervention or a concomitant medication. Overdose per se will not be reported as an AE/SAE unless it is an intentional overdose taken with possible suicidal/self-harming intent. Such overdoses should be reported regardless of sequelae.
- The signs, symptoms, and/or clinical sequelae resulting from lack of efficacy will be reported as AE or SAE if they fulfill the definition of an AE or SAE. “Lack of efficacy” or “failure of expected pharmacological action” also constitutes an AE or SAE.

Events NOT Meeting the AE Definition

- Any clinically significant abnormal laboratory findings or other abnormal safety assessments which are associated with the underlying disease, unless judged by the investigator to be more severe than expected for the participant’s condition.
- The disease/disorder being studied or expected progression, signs, or symptoms of the disease/disorder being studied, unless more severe than expected for the participant’s condition.
- Medical or surgical procedure (e.g., endoscopy, appendectomy): the condition that leads to the procedure is the AE.
- Situations in which an untoward medical occurrence did not occur (social and/or convenience admission to a hospital).

- Anticipated day-to-day fluctuations of pre-existing disease(s) or condition(s) present or detected at the start of the study that do not worsen.

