2.3. Benefit/Risk Assessment

Some participants may experience discomfort when completing assessments related to their stress levels and emotional well-being. Although participation in this study may reduce stress and improve emotional well-being, we recognize that individuals experiencing high stress may conversely face the risk of symptomatic worsening. Both text message platforms are two-way. This will allow for review of the evaluation of content and assessment to determine if participants are experiencing a worsening of stress and are in need of further support.

3. Objectives and Endpoints

Objectives	Outcomes

Primary
 
 • Feasibility of recruitment including eligibility rates and acceptance rates • Feasibility of delivering the intervention via text message • Acceptability of the intervention including dropout rates, percentage of completed assessments, adherence, and estimates of satisfaction 	
The main outcome of the FACE STRESS study is to evaluate feasibility and acceptability of an EMA and EMA plus text message intervention. Specifically, we will evaluate:
 
 • proportion of individuals who will contact us because interested to participate • the number of eligible individuals after the initial screening • time taken to recruit the sample • retention rates • the number and percentage of participants responding to any EMA text over the 3-week study • Satisfaction will be measured using both open-ended questions and likert-scaled questions to examine the acceptability and utility of the both EMA and intervention texts.

Secondary
 
 • Explore indicators of the EMA and text message intervention efficacy The effect sizes on reductions in perceived stress and other psychological symptoms will be estimated in the EMA and EMA+intervention groups at post-intervention, 1, 3 and 6-month time-points. 	
Secondary outcomes will measure:
 
 • Perceived stress and psychological overload • symptoms of anxiety and depression • symptoms of PTSD • positive and negative affects • resilience • psychological well-being

4. Study Design

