4.1. Overall Design

This study is a pilot randomized controlled trial with embedded qualitative research. Eligible participants who complete an informed consent form will be randomized to receive 3 weeks of EMA or 3 weeks of EMA plus the text message intervention for stress management based on a 1:1 allocation using random block sizes of 2.

Eligible participants will sign the consent form online before moving on to complete their baseline assessment. All participants will receive a copy of their signed consent form and will be provided with the research personnel's contact details. Participants who do not complete the baseline survey within 3 days from enrollment will be excluded from the study. Once their baseline is completed, participants will be randomized to receive:

- **Control:** 3 weeks of EMA, consisting of 2 text messages per day delivered at random times during waking hours to prompt participants to complete the survey
- **Intervention:**
 - o 1 week of EMA, consisting of 2 text messages per day delivered at random times during waking hours to prompt participants to complete the survey followed by
 - o 2 additional weeks of EMA in combination with 2 text messages per day with content related to stress management techniques.

At the end of the 3 weeks, participants in both groups will complete a post-intervention survey designed to evaluate participant satisfaction and to gather information for the purposes of improving the content of the text-message intervention. Changes in levels of psychological distress and well-being from baseline will be also evaluated.

At 1, 3 and 6-months post intervention, participants will be contacted via text message to complete a follow up survey. The follow up survey will include the same information collected at baseline with the exclusion of age, race, gender and adverse childhood events.

Participants from either group will be informed that they can withdraw from the study at any time without giving a reason by replying 'STOP' to any of the messages, or by contacting a member of the research team. No further information will be collected from participants who withdraw from the study.

Participants in the control group will be offered the opportunity to receive the intervention after the 6 months follow-up period. No data will be collected from this intervention.

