5.1. Inclusion Criteria

Participants are eligible to be included in the study only if all of the following criteria apply:

1. Age 22 or older
2. Must reside in an Eastern Standard Time or Central Standard Time zone
3. Able to read and write in English as demonstrated by review and completion of an Informed Consent Form
4. Own an SMS enable smartphone (Android or iPhone OS4)
5. Scoring >5 on the 4-item Perceived Stress Scale (reflecting higher-than-average perceived stress; 15, 16)

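### Section 10.3.1 makes stress that persists without worsening both an adverse event and not one, and non-response could be recorded more readily in the intervention arm

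*Combined protocol and SAP*

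**What the plan says.** Two lists in Section 10.3.1 bear on the point.

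Among events that meet the AE definition, one bullet has two sentences on lack of efficacy. The first is conditional: "The signs, symptoms, and/or clinical sequelae resulting from lack of efficacy will be reported as AE or SAE if they fulfill the definition". The second says that lack of efficacy, or failure of the expected pharmacological action, "also constitutes an AE or SAE". It carries no condition. The same list also includes a pre-existing condition that becomes more frequent or more intense.

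Among events that do not meet the definition are:
- "The disease/disorder being studied or expected progression, signs, or symptoms of the disease/disorder being studied, unless more severe than expected for the participant’s condition"
- "Anticipated day-to-day fluctuations of pre-existing disease(s) or condition(s) present or detected at the start of the study that do not worsen"

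Section 5.1 requires every participant to have raised stress at entry: "Scoring >5 on the 4-item Perceived Stress Scale (reflecting higher-than-average perceived stress". Under Section 4.1 the control arm receives "3 weeks of EMA, consisting of 2 text messages per day delivered at random times during waking hours to prompt participants to complete the survey". The intervention arm adds stress-management texts in the last two of its three weeks. Section 6.6 offers controls the intervention only after the 6-month follow-up. Section 6.3 marks blinding as not applicable.

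**The concern.** Raised stress that does not improve is the ordinary form of non-response in this trial. Whether it is an adverse event depends on which list the assessor applies, and the protocol does not say which prevails.

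The assessor knows the arm. Lack of efficacy attaches most naturally to participants who were sent stress-management content; a control participant has been sent survey prompts only. An assessor acting in good faith could therefore record non-response in the intervention arm and leave the same outcome unrecorded in control. Adverse event counts would then partly restate the stress results, and a reader could not tell a safety finding from a lack of benefit.

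**Working it through.** The plan gives no figure to reproduce, so the check is mainly a comparison of texts. Take three courses that a participant's stress might follow and apply the two lists in Section 10.3.1 to each.

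| Course of stress | Events that count | Events that do not count | Result |
|---|---|---|---|
| Improves | No rule applies | Not needed | Not an AE |
| Unchanged, no worsening | AE, under the unconditional lack-of-efficacy sentence | Excluded: symptom of the studied condition, not more severe than expected; also excluded if seen as non-worsening fluctuation | Contradiction |
| Worsens beyond expectation | AE, as exacerbation of a pre-existing condition | Exclusion lifts | AE, in either arm |

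Only the middle row is in conflict. Unchanged stress is neither new nor exacerbated, so the general definition that opens the section does not reach it. It enters only through the unconditional sentence.

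**Arms.** Nothing in Section 10.3.1 restricts the rule by arm, and Section 8.3.1 collects adverse events from consent to 6 months in everyone. The possible asymmetry comes from three other facts: only one arm receives the content whose efficacy is in question (Sections 4.1 and 6.6), the efficacy question in Section 2.1 concerns the text message intervention, and there is no blinding (Section 6.3).

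**Scale, as an illustration only.** Suppose that every intervention participant with no reduction in stress were recorded. Assume a mean reduction of 0.2 to 0.5 SD and an SD of change of 0.8 to 1.0; neither is in the documents. The share with no reduction is Phi(-mean reduction / SD of change):
- Phi(-0.2 / 1.0) = Phi(-0.20) = 0.42, and 0.42 x 35 = about 15 participants
- Phi(-0.5 / 0.8) = Phi(-0.625) = 0.27, and 0.27 x 35 = about 9 participants

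Under the exclusion list, the count from merely persistent stress is 0 in both arms. The 9 to 15 of 35 shows what literal application could produce under these assumptions. It is not a forecast, because the protocol does not derive adverse events from questionnaire scores.

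**The case against.** The strongest reply is that this is leftover template text with little consequence. The sentence speaks of pharmacological action in a trial that gives no drug, and the sentence before it limits reporting to symptoms that meet the AE definition. Adverse events are participant-reported (Section 8.3) and sought by open-ended questions (Section 8.3.2), so few people would report that they feel no better. Section 9.4.1 plans coding and the use of the Safety Population, with no between-arm test. Adverse events are not among the primary or secondary outcomes, and Section 8.2 requires each to be classified by its relationship to the intervention.

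Most of this stands, and it keeps the point minor. It does not remove the contradiction. The second sentence is worded as an additional route and drops the condition in the first. Section 8 makes adherence to the protocol's requirements essential and allows no waivers, so the plan cannot rely on staff to disregard a written rule.

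Two stronger readings are tempting, and the documents do not support them.

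- A reader might infer that the symptomatic worsening named as a risk in Section 2.3 ("individuals experiencing high stress may conversely face the risk of symptomatic worsening") falls between the two lists. It does not. Exacerbation of a pre-existing condition is listed as an AE, the studied-condition exclusion lifts when severity exceeds expectation, and the fluctuation exclusion covers only fluctuations that do not worsen. Judging what severity was expected remains a matter for the investigator, but the wording is the same for both arms.
- A reader might infer that only the intervention arm can have such events and that control would have none. No rule says so. Sections 1.1 and 3 plan effect sizes for stress reduction in both groups, so an assessor could record lack of efficacy for an EMA-only participant. If the sentence were applied in both arms, the imbalance could vanish or even reverse.

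**Conclusion.** The contradiction is real and confined to stress that persists without worsening. Because every participant enters with raised stress, it concerns a common outcome.

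That non-response could be recorded more readily in the intervention arm is a reasonable inference from the arm contents and the lack of blinding; the protocol does not state it. The size of any imbalance cannot be derived from the documents: it depends on how many participants do not improve, how many mention it, and how the assessor reads the rule in each arm. The illustrative 9 to 15 of 35 rests on an assumed effect, an assumed SD of change and complete recording.

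This is a drafting inconsistency of low severity, worth correcting because the correction is nearly free.

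**What to change.** Reconcile the two lists in Section 10.3.1 so that one rule for persistent stress applies identically in both arms. One way is to delete the unconditional lack-of-efficacy sentence and keep the conditional sentence before it. Symptoms that meet the AE definition then remain reportable. Worsening remains reportable under the existing exacerbation and more-severe-than-expected wording, so no new worsening rule is needed. Non-improvement is captured by the stress outcomes already collected in both arms at post-intervention and at 1, 3 and 6 months.

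The cost is the removal of one sentence, with no added data collection and no change to sample size or analysis.
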